6.18. Clinical Trial Registry Analyses

Additional analyses will be performed for the purpose of fulfilling the Clinical Trial Registry (CTR) requirements.

Analyses provided for the CTR requirements include the following:

Summary of adverse events, provided as a dataset which will be converted to an XML file. Both Serious Adverse Events and 'Other' Adverse Events are summarized: by treatment group, by MedDRA preferred term.

- An adverse event is considered 'Serious' whether or not it is a treatment emergent adverse event (TEAE).

- An adverse event is considered in the ‘Other’ category if it is both a TEAE and is not serious. For each Serious AE and ‘Other’ AE, for each term and treatment group, the following are provided:
 - the number of participants at risk of an event
 - the number of participants who experienced each event term
 - the number of events experienced.
- Consistent with www.ClinicalTrials.gov requirements, ‘Other’ AEs that occur in fewer than 5% of subjects/subjects in every treatment group may not be included if a 5% threshold is chosen (5% is the minimum threshold).
- AE reporting is consistent with other document disclosures for example, the CSR.

7. Unblinding Plan

This is a double-blind study during the Induction Period. Induction dose cohort assignment will remain blinded throughout the study; however, during the Maintenance Period, dosing strategy (PRN or Q8W) will be open label. To preserve the blinding of the study, a minimum number of Lilly personnel will see the randomization table and treatment assignments before the study is complete.

To minimize any bias being introduced into the analysis of the study results, the SAP and PK/PD analysis plan will be finalized and approved before the Interim Analysis 1 (Primary Analysis) is implemented. A limited number of pre-identified individuals at Lilly may gain access to the unblinded data as part of the prespecified interim analysis (see Section 6.17 and the [Study AMAF Blinding and Unblinding Plan](#)). Information that may potentially unblind the study during the analyses will not be shared with study sites until the entire study has been unblinded.

A study blinding and unblinding plan will be finalized prior to first unblinded data transfer.

8. References

Appendix 1. Simulation for Logistic Regression with Firth Correction

When PBO response rate is small and there are zero cell values, logistic regression will over estimate variance resulting in larger *p*-values and reduced power. Logistic regression with a Firth correction adjusts for small sample sizes and zero cell values. We used simulation to investigate a “two-step” approach. If there is

- “Small” number of PBO responders, then use logistic regression with Firth correction
- “Not Small” number of PBO responders, then use logistic regression without correction

LY Response Rate	Treatment Effect (LY-PBO)	Single Analysis Power		“Two-Step” Approach Power			
		Logistic Regression	Logistic Regression w/ Firth Correction	≤1 PBO Responder	≤2 PBO Responder	≤3 PBO Responder	≤4 PBO Responder
0.03	0.00	<0.001	<0.001	<0.001	<0.001	<0.001	<0.001
0.05	0.02	0.002	0.002	0.002	0.002	0.002	0.002
0.10	0.07	0.063	0.075	0.075	0.075	0.075	0.075
0.15	0.12	0.277	0.363	0.372	0.369	0.363	0.363
0.20	0.17	0.535	0.683	0.695	0.694	0.684	0.683
0.25	0.22	0.709	0.892	0.901	0.899	0.893	0.893
0.30	0.27	0.783	0.981	0.984	0.984	0.982	0.982
0.35	0.32	0.793	0.993	0.994	0.994	0.993	0.993
0.40	0.37	0.798	0.999	0.999	0.999	0.999	0.999
0.45	0.42	0.798	0.999	0.999	0.999	0.999	0.999
0.50	0.47	0.799	>0.999	>0.999	>0.999	>0.999	>0.999
0.55	0.52	0.799	>0.999	>0.999	>0.999	>0.999	>0.999
0.60	0.57	0.799	>0.999	>0.999	>0.999	>0.999	>0.999

Results showed that logistic regression with Firth correction increased the power by ~10% compared to the ones without Firth correction when the treatment difference is >7%. Therefore, it is suggested to apply Firth correction in the logistic regression models in Study AMAF.

Appendix 2. Study Visit Definition for Psoriasis Symptoms Scale (PSS)

Psoriasis Symptoms Scale (PSS) is collected as a daily diary, entries will be mapped to study week by the following:

Week ^a	Start Day ^b	End Day
Baseline	-7	-1
Week 1	Max(Baseline Assessment Date, Week 2 Assessment Date – 14)	Week 2 Assessment Date - 8
Week 2	Max(Baseline Assessment Date, Week 2 Assessment Date – 7)	Week 2 Assessment Date - 1
Week 3	Max(Week 2 Assessment Date, Week 4 Assessment Date – 14)	Week 4 Assessment Date -8
Week 4	Max(Week 2 Assessment Date, Week 4 Assessment Date – 7)	Week 4 Assessment Date – 1
Week 5	Max(Week 4 Assessment Date, Week 8 Assessment Date – 28)	Week 8 Assessment Date -22
Week 6	Max(Week 4 Assessment Date, Week 8 Assessment Date – 21)	Week 8 Assessment Date -15
Week 7	Max(Week 4 Assessment Date, Week 8 Assessment Date – 14)	Week 8 Assessment Date -8
Week 8	Max(Week 4 Assessment Date, Week 8 Assessment Date – 7)	Week 8 Assessment Date – 1
Week 9	Max(Week 8 Assessment Date, Week 12 Assessment Date – 28)	Week 12 Assessment Date -22
Week 10	Max(Week 8 Assessment Date, Week 12 Assessment Date – 21)	Week 12 Assessment Date -15
Week 11	Max(Week 8 Assessment Date, Week 12 Assessment Date – 14)	Week 12 Assessment Date -8
Week 12	Max(Week 8 Assessment Date, Week 12 Assessment Date – 7)	Week 12 Assessment Date – 1
Week 13	Max(Week 12 Assessment Date, Week 16 Assessment Date – 28)	Week 16 Assessment Date -22
Week 14	Max(Week 12 Assessment Date, Week 16 Assessment Date – 21)	Week 16 Assessment Date -15
Week 15	Max(Week 12 Assessment Date, Week 16 Assessment Date – 14)	Week 16 Assessment Date -8
Week 16	Max(Week 12 Assessment Date, Week 16 Assessment Date – 7)	Week 16 Assessment Date – 1
Week 32	211	238
Week 52	351	378
Week 104	715	742

^a If End Day < Start Day, do not assign specified visit week

^b Assessment Date is the date of the specified visit week's PASI assessment

If range is at least 4 days and contains at least 4 daily entries, calculate the visit week assessment.

If more than 7 days is available between assessment dates, use only the last 7 days.

If multiple PSS assessments on a single day are present, use the latest assessment.

Leo Document ID = 3f78032b-b3d5-4290-8b81-373f1f393350

Approver: [REDACTED]
Approval Date & Time: 28-Jun-2017 00:33:13 GMT
Signature meaning: Approved

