PPD/QuantIFERON-TB Gold (per local guidelines)	X							Subjects will return 2 to 3 days after Visit 1 to have their PPD test read.
ECGs	X						X	This should be completed prior to any study dose administration or blood draw. Subjects should be supine for approximately 5 to 10 minutes before ECG collection and remain supine but awake during ECG collection.
C-SSRS	X	X	X	X	X	X	X	
CCI [REDACTED]		■	■	■	■	■	■	[REDACTED]
Study drug dosed		X			X		X	At Week 16, subjects will only receive study drug dosing if PASI <90.

Induction Dosing Period (Visits 1-7)								
Visit No.	V1	V2	V3	V4	V5	V6	V7	Comments
Week Relative to Study Drug Start	-4	0	2	4	8	12	16	All activities should be completed prior to any study dose administration unless otherwise stated below.
Day with Visit Tolerance Interval	≤28 from V2	0	14 ± 2	28 ± 3	56 ± 5	84 ± 5	112 ± 5	Visit 1 procedures may be conducted over more than 1 day as long as all tasks are completed within the allowable visit tolerance (at least 3 days should be allowed for receipt of laboratory test results).
Clinical Efficacy								
PASI	X	X	X	X	X	X	X	
sPGA	X	X	X	X	X	X	X	
PSSI, if applicable		X	X	X	X	X	X	Once a subject experiences symptoms related to scalp involvement, this form should be completed at all remaining indicated visits.
Whole body photographs		X					X	If subject has agreed to whole body photographs.
Health Outcomes								
PSS	Electronic Diary Taken Daily from Screening (V1) up to Week 16 (V7)						X	
PatGA		X	X	X	X	X	X	
DLQI		X	X	X	X	X	X	
SF-36		X					X	
Laboratory Tests								
Hematology	X	X	X	X	X	X	X	Unscheduled blood chemistry and hematology panels may be performed at the discretion of the investigator.
Lymphocyte subsets		X					X	
Serum chemistry	X	X	X	X	X	X	X	Unscheduled blood chemistry and hematology panels may be performed at the discretion of the investigator.
Urinalysis	X	X			X		X	

Induction Dosing Period (Visits 1-7)								
Visit No.	V1	V2	V3	V4	V5	V6	V7	Comments
Week Relative to Study Drug Start	-4	0	2	4	8	12	16	All activities should be completed prior to any study dose administration unless otherwise stated below.
Day with Visit Tolerance Interval	≤28 from V2	0	14 ± 2	28 ± 3	56 ± 5	84 ± 5	112 ± 5	Visit 1 procedures may be conducted over more than 1 day as long as all tasks are completed within the allowable visit tolerance (at least 3 days should be allowed for receipt of laboratory test results).
HBsAg, HBcAb, HBsAb	X							

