### **9.1.4. Health Outcomes Assessments**

The following patient-reported questionnaires will be administered according to the Schedule of Activities (Section 2) in countries where the questionnaires have been translated into the native language of the region and linguistically validated. They should be completed before administration of study drug; before the subject's clinical examination; before the subject receives any tests or results; and before the subject's health, health data, or emotions are discussed.

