6.1.2.2. Definition of Study Baseline

For efficacy, health outcomes, and safety analyses, study baseline is defined as the last non-missing assessment (including unscheduled visits) before the first injection, which in most cases will be the measure recorded at Week 0 (Visit 2). For efficacy/health outcome measures, if the patient does not take any injection, the last available value on or prior to randomization date will be used.

For PSS, the weekly average of at least 4 days of the consecutive 7 days prior to the first injection will be the study baseline score.

In cases where baseline measurements are taken on the same day as injection and no times are recorded, it will be assumed that these measurements are taken prior to the injection.

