PSS	
The Psoriasis Symptoms Scale (PSS) is a patient-administered assessment of 8 symptoms: itch, pain, discomfort, stinging, burning, redness, scaling, and cracking. Respondents are asked to answer the questions based on their psoriasis symptoms.
 
The overall severity for each individual symptom from patient’s psoriasis is indicated by selecting the number from an NRS of 0 to 10 that best describes the worst level of each symptom in the area in the past 24 hours, where 0 (= no severity) and 10 (worst imaginable severity).
 
The symptom severity scores, ranging from 0 to 10, are the values of the selected numbers indicated by the patient on the instrument’s horizontal scale. Each of the 8 individual items will receive a score of 0 to 10 and will be reported as item scores for itch, pain, discomfort,
	PSS total score	
The PSS total score will be calculated by summing the individual item scores as follows: PSS = itch NRS + pain NRS + discomfort NRS + stinging NRS + burning NRS + redness NRS + scaling NRS + cracking NRS
	If any item score are missing, the PSS total score is missing
		PSS change from baseline	
Change from baseline = Observed PSS Total Score – Baseline PSS Total Score A negative change indicates improvement and a positive change indicates deterioration of the condition.
	Missing if either observed or baseline PSS total score is missing
		PSS item scores	The PSS score for each item as reported in daily diaries from visit1 up to visit 7, then on the tablet device at visits 7, 11, 16 and 28 (see Appendix 2).	Missing if the PSS score for the item is missing
		Change from baseline for item scores	
Change from baseline = Observed PSS Item Score – Baseline PSS Item Score A negative change indicates improvement and a positive change indicates deterioration of the condition.
	Missing if either observed or baseline item PSS score is missing

Measure	Description	Variable	Derivation / Comment	Imputation Approach if with Missing Components
	stinging, burning, redness, scaling, and cracking. In addition, a total score ranging from 0 (no psoriasis symptoms) to 80 (worst imaginable psoriasis symptoms) will be reported.			

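### SAP Appendix 2 scores the injection-day PSS entry as treated Week 1 when Visit 3 falls on Day 12 to 14, and assigns the PSS scheduled at Visit 7 to no week

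*SAP*

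**What the plan says.** **Baseline.** SAP 6.1.2.2 has a PSS-specific rule: "the weekly average of at least 4 days of the consecutive 7 days prior to the first injection will be the study baseline score". Appendix 2 tabulates the same days, -7 to -1. For measurements in general, the same section says of untimed values on the injection day that "it will be assumed that these measurements are taken prior to the injection".

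**Week 1.** In Appendix 2 the start day is "Max(Baseline Assessment Date, Week 2 Assessment Date" less 14 days, whichever is later. The end day is the Week 2 Assessment Date less 8. An Assessment Date is the date of that visit's PASI.

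**Week 16.** The window ends the day before the Week 16 Assessment Date. The next window, Week 32, opens on Day 211.

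**Collection.** The protocol's Schedule of Activities has a daily electronic diary from Visit 1 to Visit 7, and a separate PSS mark at Visit 7. SAP Table 6.2 describes diary collection up to Visit 7, "then on the tablet device at visits 7, 11, 16 and 28". On questionnaires, Protocol 9.1.4 says: "They should be completed before administration of study drug". The PSS asks for the worst level over the past 24 hours.

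**Evaluability.** A weekly score needs a window of at least 4 days and at least 4 daily entries. If more than 7 days lie between assessment dates, only the last 7 are used. If a day has several entries, the latest is used.

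**The concern.** At nominal timing, Appendix 2 places the entry made on a visit day in the week that follows the visit. Within induction this only shifts a day between adjacent weeks. At the two ends it does more:

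- On the day of first injection, the following week is the first treated week. An entry that the SAP's general rule would treat as pre-injection if untimed, and whose recall period reaches back before the injection in any case, is averaged into a post-treatment score.
- At Visit 7 there is no following week, so a scheduled measurement falls outside every window.

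Mean PSS change at Week 16 is a secondary endpoint, and SAP Table 6.3 compares PSS change with placebo at all postbaseline induction visits. At stake are a diluted Week 1 change and the use of an entry already collected on the date of a secondary endpoint.

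**Working it through.** **Inputs.** Visit 2 is Day 0. The Schedule allows Visit 3 on Day 14 ± 2, Visit 6 on Day 84 ± 5 and Visit 7 on Day 112 ± 5. The window limits and the 4-entry rule are from Appendix 2. Diary adherence is not given, so daily completion c = 0.6 to 0.9, independent between days, is an assumption.

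**Step 1: the plan's own baseline window.** Days -7 to -1 are 7 days. This agrees with SAP 6.1.2.2.

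**Step 2: Week 1.** Start = max(0, V3 - 14); end = V3 - 8.

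| Visit 3 | Week 1 window | Days | Day 0 included | Day 0 weight, full diary |
|---|---|---|---|---|
| Day 12 | 0 to 4 | 5 | yes | 1/5 |
| Day 13 | 0 to 5 | 6 | yes | 1/6 |
| Day 14 | 0 to 6 | 7 | yes | 1/7 |
| Day 15 | 1 to 7 | 7 | no | none |
| Day 16 | 2 to 8 | 7 | no | none |

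With the minimum four entries, the Day 0 weight can reach 1/4. If the Day 0 entry carries no treatment effect, a subject's Week 1 change is multiplied by 1 - w, where w is that weight. The loss is 14% at w = 1/7, 20% at 1/5 and 25% at 1/4. With Visit 3 on Day 15 or 16, the Day 0 entry is in neither baseline nor Week 1.

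**Step 3: Week 16.** Start = max(V6, V7 - 7); end = V7 - 1. With Visit 6 on Day 79, 84 or 89 and Visit 7 on Day 107, 112 or 117, all nine combinations give the 7 days before Visit 7 and leave out Visit 7 itself. The latest permitted Visit 7 is Day 117 and Week 32 opens on Day 211, so no later window picks it up.

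**Step 4: missing Week 16 scores.** With X the number of diary days completed:

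- As planned, the score is missing if X ≤ 3 of 7.
- Seven calendar days ending on Visit 7 (six diary days plus a completed Visit 7 entry): missing if X ≤ 2 of 6.
- Eight days (seven diary days plus a completed Visit 7 entry): missing if X ≤ 2 of 7.

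| c | As planned | Seven days incl. Visit 7 | Eight days incl. Visit 7 |
|---|---|---|---|
| 0.6 | 29.0% | 17.9% | 9.6% |
| 0.7 | 12.6% | 7.0% | 2.9% |
| 0.8 | 3.3% | 1.7% | 0.5% |
| 0.9 | 0.3% | 0.1% | <0.1% |

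Of 200 randomized subjects, the seven-day version would recover about 22, 11, 3 and 0.3 scores at these four values. The eight-day version would recover about 39, 19, 6 and 0.5.

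**The case against.** The best defence is that the plan is consistent where it matters most. Appendix 2 reproduces the PSS baseline rule in 6.1.2.2, and Week 16 uses the matching seven days before its visit, so the two are like for like. This stands. Three further points also stand:

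- Week 1 is neither a scheduled visit nor a named endpoint. At most one entry is affected, by the same rule in every arm.
- The Week 16 change from baseline does not use the Day 0 entry.
- The main PSS analysis in induction is an MMRM, so a subject with a baseline and earlier weekly scores contributes even without a Week 16 score.

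A reader might infer more than the documents support:

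- **That evaluable baseline or Week 16 scores are lost.** They are not: anyone with four of seven entries keeps both. Only subjects short of entries could gain. One such case is a subject screened on Day -3, who can have at most three baseline entries (Days -3, -2, -1) even with a perfect diary. The documents do not show how many subjects are screened that late.
- **That the Day 0 entry is a known pre-dose, on-site measurement.** No site PSS is marked at Visit 2. It is a diary entry with no stated time of day, and because the latest entry of a day is used, it may follow the injection. The 24-hour recall still makes it largely a pre-injection report.
- **That Week 1 always contains it.** This depends on Visit 3 falling on Day 12, 13 or 14.

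None of this explains why a PSS scheduled at Visit 7 has no window, or why the injection day should open a treated week.

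**Conclusion.** Both mapping defects are in the text, and both are minor. With Visit 3 on Day 12 to 14, the injection-day entry supplies 1/7 to 1/5 of a full-diary Week 1 mean and at most 1/4, pulling Week 1 change toward zero if that entry reflects the untreated state. The Visit 7 PSS is always left out.

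The effect on Week 16 completeness depends on adherence, which the documents do not give. It is negligible at 90% daily completion and becomes material only near 70% or below. The figures assume independent days and a Visit 7 entry that is always completed. They do not show bias in the Week 16 comparison.

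**What to change.** In Appendix 2:

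1. Start the Week 1 window no earlier than the day after first injection, keeping the Week 2 date less 14 as the alternative limit.
2. End the Week 16 window on the Week 16 Assessment Date, so that the pre-dose Visit 7 PSS counts. Name that entry as the one used if a diary entry exists on the same day, since the latest-entry rule could otherwise select a post-dose value.
3. State whether Week 16 then spans seven or eight days. Eight days cannot remove a score but needs an exception to the last-7-days rule. Seven days keeps that rule, but a subject who misses the Visit 7 entry could fall below four.
4. Only if an injection-day entry timed before the injection is also to count toward baseline, change SAP 6.1.2.2 to match. Changing Appendix 2 alone would contradict it.

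The cost is a few lines of SAP text and no new data. One Week 16 entry would come from the tablet and not the diary, and unless baseline is changed too, the two windows no longer match exactly. With Visit 3 on Day 12, Week 1 shrinks to Days 1 to 4, which still meets the four-day minimum but then needs all four entries.

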Maintenance Dosing Period (Visits 19-29)												
Visit No.:	V19	V20	V21	V22	V23	V24	V25	V26	V27	V28	V29	Comments
Week Relative to Study Drug Start	64	68	72	76	80	84	88	92	96	100	104	All activities should be completed prior to any study dose administration unless otherwise stated below.
Day with Visit Tolerance Interval	448 ± 5	476 ± 5	504 ± 5	532 ± 5	560 ± 5	588 ± 5	616 ± 5	644 ± 5	672 ± 5	700 ± 5	728 ± 5	
CCI			■			■			■		■	

Follow-up Period (Visits 801-804)					
Visit No.:	V801 a	V802 a	V803 a	V804/ET	Comments
Week Relative to Study Drug Start	108	112	116	120	All activities should be completed prior to any study dose administration unless otherwise stated below.
Day with Visit Tolerance Interval	756 ± 5	784 ± 5	812 ± 5	840 ± 5	
Physical examination & weight				X	All physical examinations throughout the study should include a symptom-directed evaluation as well as examination of heart, lungs, and abdomen and visual examination of all skin areas (including genitalia and breast areas).
Concomitant medications	X	X	X	X	
Adverse events	X	X	X	X	
Vital signs (BP and heart rate), body temperature only if clinically indicated	X	X	X	X	Sitting blood pressure and pulse, to be obtained at approximately the same time as ECG measurements or blood sampling. When multiple assessments are scheduled for the same time point, the order of completion should be as follows: ECG, vital signs, and then blood sampling.
ECGs				X	ECGs should be performed before any blood is drawn. Subjects should be supine for approximately 5 to 10 minutes before ECG collection and remain supine but awake during ECG collection.
C-SSRS	X	X	X	X	
CCI	■	■	■	■	
Clinical Efficacy					
PASI	X	X	X	X	
sPGA	X	X	X	X	
PSSI, if applicable	X	X	X	X	Once a subject experiences symptoms related to scalp involvement, this form should be completed at all remaining indicated visits.
Whole body photographs				X	If subject has agreed to whole body photographs.
Health Outcomes					
PSS				X	
PatGA				X	
DLQI				X	
SF-36				X	
Laboratory Tests					

Follow-up Period (Visits 801-804)					
Visit No.:	V801 a	V802 a	V803 a	V804/ET	Comments
Week Relative to Study Drug Start	108	112	116	120	All activities should be completed prior to any study dose administration unless otherwise stated below.
Day with Visit Tolerance Interval	756 ± 5	784 ± 5	812 ± 5	840 ± 5	

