## 5. Study Design

### 5.1. Overall Design

Study AMAF is a multicenter, randomized, parallel-arm, placebo-controlled trial with 4 study periods in subjects with moderate-to-severe plaque psoriasis.

[figure not shown]
**Screening Period (≤4 weeks):** Subjects will be evaluated for study eligibility ≤28 days before the baseline visit (Visit 2/Week 0). At the baseline visit (Visit 2), subjects who fulfill the eligibility criteria will be randomized to 1 of 4 induction treatment arms.

**Induction Period (16 weeks):** A double-blind, 16-week induction period is designed to establish the efficacy and safety of LY3074828 administered at Visit 2 (Week 0) and Visit 5 (Week 8). Subjects will be randomized to 1 of 4 induction treatment arms (LY3074828 30 mg SC, LY3074828 100 mg SC, LY3074828 300 mg SC, and placebo every 8 weeks [Q8W]) stratified on the basis of previous exposure to biologic therapy for treatment of psoriasis.

**Maintenance Period (88 weeks):** The maintenance period consists of 88 weeks of treatment. At the end of the induction period (Week 16), subjects will continue treatment in the maintenance period which is intended to explore 1 of 2 treatment strategies through Week 104. All placebo subjects and subjects assigned to treatment with LY3074828 who have a <90% improvement in Psoriasis Area and Severity Index (PASI) from baseline (PASI 90) at Week 16 will receive LY3074828 300 mg SC Q8W during the entire maintenance period. Subjects with ≥PASI 90 (as needed [PRN] dosing group) at Week 16 will only be dosed with LY3074828 at the baseline dose level assignment no more frequently than Q8W when disease activity level is <PASI 90, and this will continue until ≥PASI 90 is regained. See Section 7.8.2 for maintenance period rescue treatment.

Subjects who complete Week 104 (Visit 29) of Study AMAF may be eligible to receive additional LY3074828 treatment by choosing to enroll in a separate long-term extension study, pending competent authority and/or ethical review board (ERB) approvals to conduct the separate long-term extension study.

**Follow-up Period (16 weeks):** Subjects who do not enroll in the separate long-term extension study will complete the follow-up period of Study AMAF. The follow-up period will include a visit every 4 weeks for a total of 16 weeks following Visit 29 to assess subject safety and study drug efficacy. [Figure AMAF.1](#) illustrates the study design.

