6.1.2. Definitions

6.1.2.1. Study Time Intervals

Induction Period

All subjects who were randomized to the study are considered as entering the Induction Period.

The start of the Induction Period is defined as the date of first injection following randomization. For subjects who were randomized but not dosed, the Induction Period starts at the randomization date.

The end of the Induction Period is defined as the date of PASI measurement at Week 16, or the early termination date if subjects discontinued from study prior to or at Week 16, or Day 117, whichever comes first.

Maintenance Period

All subjects who had Week 16 visit with PASI measurement (except the ones discontinued the study at Week 16) are considered to have entered the Maintenance Period.

The start of the Maintenance Period is defined as the same date as end of the Induction Period, which is the date of PASI measurement at Week 16.

The end of the Maintenance Period is defined as the visit date at Week 104, or the date when the subjects received rescue treatment, or the early termination date if subjects discontinued from study prior to or at Week 104, whichever comes first.

Rescue Period

All subjects in PRN groups who received at least 1 dose of rescue treatment are considered to have entered the Rescue Period, and will be included in the Rescue Period analysis population.

The start of the Rescue Period is defined as the date the patient received the first dose of rescue treatment.

The end of the Rescue Period is defined as the visit date at Week 104, or early termination date if subjects discontinued from study prior to or at Week 104, whichever comes first.

Follow-up Period

All subjects who had Visit 29 are considered to have entered the Follow-up Period, and will be included in the Follow-up Period analysis population.

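### SAP Appendix 2's four-daily-entries rule, read as written, gives no PSS score at Weeks 32, 52 or 104; Table 6.2's Visit 28 misses the Week 104 window; and Week 120 has no window

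*SAP*

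**What the plan says.** Change from baseline in PSS at Weeks 52, 104 and 120 is a secondary endpoint in the protocol Synopsis and a secondary objective in SAP Section 4.2.

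- **Collection.** The PSS row of the induction table in the protocol's Schedule of Activities reads "Electronic Diary Taken Daily from Screening (V1) up to Week 16 (V7". After that PSS is marked at individual visits, including Visit 11 (Week 32), Visit 16 (Week 52) and Visit 804 (Week 120).
- **SAP Table 6.2.** PSS item scores are "as reported in daily diaries from visit1 up to visit 7, then on the tablet device at visits 7, 11, 16 and 28", with a pointer to Appendix 2.
- **SAP Appendix 2.** The lead sentence covers the whole table: "Psoriasis Symptoms Scale (PSS) is collected as a daily diary, entries will be mapped to study week by the following". The rows run from baseline through Weeks 1 to 16 and then give Week 32 (Days 211-238), Week 52 (Days 351-378) and Week 104 (Days 715-742). Below the table stands the rule "If range is at least 4 days and contains at least 4 daily entries, calculate the visit week assessment". Two further rules keep only the last 7 days of a longer interval and only the latest entry on any one day.
- **Visit numbering.** Protocol Section 5.1 fixes the Week 104 visit: "Subjects who complete Week 104 (Visit 29) of Study AMAF may be eligible".

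**The concern.** The only written derivation of a PSS visit score asks for four daily entries, and it is applied to weeks when the diary has already stopped. A programmer following Appendix 2 exactly would have no Week 52 or Week 104 PSS score to summarise. A programmer who uses the tablet value overrides the rule without written authority. The visit named in Table 6.2 for the last maintenance assessment does not match the window in Appendix 2, and the SAP gives no way to map or analyse the Week 120 assessment. At stake are the long-term PSS summaries, which are secondary endpoints.

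**Working it through.** **Inputs.** Visit days and the ±5-day tolerance come from the protocol's Schedule of Activities. Windows and rules come from SAP Appendix 2.

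**Step 1: reproduce the SAP's windows.** With nominal day = 7 × week, all three follow nominal day −13 to +14, which is 28 days:

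- Week 32: 224 − 13 = 211; 224 + 14 = 238
- Week 52: 364 − 13 = 351; 364 + 14 = 378
- Week 104: 728 − 13 = 715; 728 + 14 = 742

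**Step 2: count the scheduled visits in each window** (visit interval = nominal day ± 5, first dose = Day 0).

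| Window | Visit before | Visit inside | Visit after | Scheduled entries | Required |
|---|---|---|---|---|---|
| Week 32: 211-238 | V10: 191-201 | V11: 219-229 | V12: 247-257 | 1 | 4 |
| Week 52: 351-378 | V15: 331-341 | V16: 359-369 | V17: 387-397 | 1 | 4 |
| Week 104: 715-742 | V28: 695-705 | V29: 723-733 | V801: 751-761 | 1 | 4 |

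The same-day rule keeps one entry per day, so one visit gives at most one entry. Moving every visit by +1 (first dose = Day 1) leaves the same single visit in each window.

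**Step 3: the last-7-days rule.** If it were applied to these windows it would keep Days 232-238, 372-378 and 736-742. All three stretches fall after the scheduled visit intervals, so this rule cannot sensibly apply to the late rows either.

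**Step 4: Visit 28.** Its interval is 700 ± 5 = Days 695-705. The gap to the Week 104 window is 715 − 705 = 10 days, or 715 − 706 = 9 days if first dose is Day 1. SAP Section 6.1.2.1 ends induction at the latest by "or Day 117, whichever comes first". Since 112 + 5 = 117 is the upper limit of Visit 7 by Day 0 numbering, 10 is the better-supported figure. Visit 29 lies wholly inside the window.

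**Step 5: Week 120.** Visit 804 is Day 840 ± 5 = Days 835-845. The last window in Appendix 2 closes on Day 742, and Table 6.2 does not list Visit 804. The PSS rows of Table 6.3 after induction cover the Maintenance and Rescue Periods, and SAP Section 6.1.2.1 ends both by Week 104. The same −13/+14 pattern would give 840 − 13 = 827 to 840 + 14 = 854. That window contains Visit 804 and excludes Visit 803 (Days 807-817).

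**The case against.** The strongest reply is that the exemption is implied. The rule speaks of daily entries and of calculating a score. SAP Section 6.1.2.2 shows what calculation is meant: a weekly average over at least 4 of 7 consecutive days. Table 6.2 separates diary from tablet, the late rows have fixed 28-day windows where the post-baseline diary rows run between assessment dates, and Table 6.3 plans a maintenance ANCOVA of PSS that the literal reading would leave without data. A sensible programmer would use the tablet value. This stands as evidence of intent. It does not replace a written rule, and it does not answer the Visit 28 or Week 120 points.

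Second, the count of one entry at Week 104 takes collection from the protocol's visits, where Table 6.2's Visit 28 would give none. That is true, and either count is below four. In the text available here the PSS mark in the Visit 19-29 schedule is displaced, so collection at Visit 29 is inferred from the Week 104 endpoint and Section 5.1.

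Third, a Visit 804 entry carries its visit label, and protocol Section 10.3.3.2 equates that visit with Week 120. The entry can therefore be identified; what is missing is the SAP's mapping and analysis. The readable long-term sentence in that section names DLQI, SF-36 and PatGA but not PSS, so PSS at Week 120 rests on the Synopsis and SAP Section 4.2.

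Finally, the Visit 7 tablet entry also has no home, because the Week 16 row closes the day before that visit. This is fair, and one sentence can settle it.

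**Conclusion.** The concern holds as a minor fault: the derivation is wrong as written. Followed exactly, Appendix 2 has 1 scheduled entry against 4 required in all three windows after Week 16 and derives no PSS score at Weeks 32, 52 or 104. This assumes that PSS is collected only at scheduled visits after Week 16, and it holds under either day numbering. Whichever way the rule is read, Visit 28 misses the Week 104 window by 10 days (9 if first dose is Day 1), and Week 120 has no row in Appendix 2 and no analysis in Table 6.3. The entries are still collected, so the summaries can be recovered. The primary PASI 90 analysis and the Week 16 PSS comparison are not affected.

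**What to change.** 1. **Appendix 2, rules.** Limit the four-entry rule and, for clarity, the last-7-days rule to baseline through Week 16. State that Weeks 32, 52, 104 and 120 use the single tablet entry in the window, and say whether the Visit 7 tablet entry is used.
2. **Appendix 2, windows.** Add a Week 120 row, for example Days 827-854.
3. **Table 6.2.** Reconcile Visit 28 with the Week 104 visit (Visit 29) and add Visit 804.
4. **Table 6.3.** Add a Week 120 follow-up summary. The table has no follow-up row for any measure, so the addition should cover every measure with a Week 120 secondary endpoint: PASI 75/90/100, PSS, PatGA, DLQI and SF-36. SAP Section 6.1.2.1 already says that subjects who had Visit 29 "will be included in the Follow-up Period analysis population". That population can be used, restricted to those who enter and complete follow-up as protocol Section 10.3.3.2 requires.

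The cost is SAP wording and the matching programming specification. No protocol change and no new data are needed.
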